5.10 Bleeding Patterns

The subject diary data will be used to characterize bleeding patterns. Bleeding data will be analyzed by cycle and by RP.

5.10.1 Definitions of Bleeding and Spotting

Definitions for bleeding and spotting used for the cycle and RP analysis are provided in **Table 1** below. In the diary, "0" was to be ticked for no bleeding or spotting, "1" for spotting and "2" for bleeding.

Term	Definition
Bleeding	Evidence of vaginal blood loss that requires the use of sanitary protection with a tampon, pad or pantyliner.
Spotting	Evidence of minimal vaginal blood loss that does not require new use of sanitary protection, including pantyliners.
Bleeding day	Day where bleeding (2) was reported for that day in the subject diary
Spotting day	Day where spotting (1) was reported for that day in the subject diary
Bleeding/spotting- free day	Day where no bleeding or spotting (0) was reported in the subject diary
Bleeding/Spotting episode	One or more consecutive bleeding and/or spotting days where there are both bleeding and spotting days bounded on either end by 2 bleeding/spotting-free days
Bleeding only episode	One or more consecutive bleeding days where there are no spotting days bounded on either end by 2 bleeding/spotting-free days
Spotting only episode	One or more consecutive spotting days where there are no bleeding days bounded on either end by 2 bleeding/spotting-free days
Bleeding/spotting- free episode	Two or more consecutive bleeding/spotting-free days bounded on either end by a bleeding or spotting day

Table 1: Bleeding and spotting definitions

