- The total (scheduled + unscheduled) number of days with bleeding and/or spotting (i.e. the number of bleeding days + the number of spotting days within the bleeding only, spotting only and bleeding/spotting episodes that start during the cycle of interest)
- The total (scheduled + unscheduled) number of days with bleeding only (i.e. the number of bleeding days within the bleeding only and bleeding/spotting episodes that start during the cycle of interest)
- The total (scheduled + unscheduled) number of days with spotting only (i.e. the number of spotting days within the spotting only and bleeding/spotting episodes that start during the cycle of interest)
- The number of unscheduled days with bleeding and/or spotting (i.e. the number of bleeding days + the number of spotting days within the unscheduled bleeding only, spotting only and bleeding/spotting episodes that start during the cycle of interest)
- The number of unscheduled days with bleeding only (i.e. the number of bleeding days within the unscheduled bleeding only and bleeding/spotting episodes that start during the cycle of interest)
- The number of unscheduled days with spotting only (i.e. the number of spotting days within the unscheduled spotting only and bleeding/spotting episodes that start during the cycle of interest)
- The number of scheduled days with bleeding and/or spotting (i.e. the number of bleeding days + the number of spotting days within the scheduled bleeding only, spotting only and bleeding/spotting episodes that start during the cycle of interest)
- The number of scheduled days with bleeding only (i.e. the number of bleeding days within the scheduled bleeding only and bleeding/spotting episodes that start during the cycle of interest)
- The number of scheduled days with spotting only (i.e. the number of spotting days within the scheduled spotting only and bleeding/spotting episodes that start during the cycle of interest)
- The start day for any scheduled bleeding episodes that have a start date within the cycle (if there are more than one scheduled bleeding episodes in the cycle, then only the start day of the earliest episode will be used)

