5.10.5 Bleeding Endpoints for Analyses by RP

For the analyses by RP, the evaluable RPs will be determined as described in Section 5.1.2 for each subject, missing data rules are provided in Section 5.15.2 and definitions of terminology are provided in Section 5.10.1.

The following variables will be derived for each evaluable RP and subject:

- The total number of days with bleeding and/or spotting (i.e. the number of bleeding days + the number of spotting days within the bleeding only, spotting only and bleeding/spotting episodes that start during the RP of interest)
- The total number of days with bleeding only (i.e. the number of bleeding days within the bleeding only and bleeding/spotting episodes that start during the RP of interest)
- The total number of days with spotting only (i.e. the number of spotting days within the spotting only and bleeding/spotting episodes that start during the RP of interest)
- The number of bleeding and/or spotting episodes
- The mean duration of the bleeding and/or spotting episodes
- The number of bleeding and/or spotting free episodes
- The mean duration of the bleeding and/or spotting free episodes

For the number of bleeding and/or spotting episodes in the RP, the number of episodes is defined as the number of bleeding only episodes + the number of spotting only episodes + the number of spotting/bleeding episodes with a start date during that RP. The duration of an episode is derived as the end date of the episode – start date of the episode + 1. The mean duration of episodes in the RP is derived from the duration of all episodes with a start date during that RP. The full duration of each of the episodes is used in the derivation of the mean duration, even if the episode continues beyond the end of the RP.

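### Read as bounded at both ends, SAP Table 1 places runs split by one free day, and bleeding at the end of the diary, in no episode; on any reading a woman who never bleeds has no free episode

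*SAP*

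**What the plan says.** Table 1 in SAP 5.10.1 defines three kinds of bleeding episode, all with the same bounds:

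- Spotting only: "One or more consecutive spotting days where there are no bleeding days bounded on either end by 2 bleeding/spotting-free days".
- Bleeding only: "One or more consecutive bleeding days where there are no spotting days bounded on either end by 2 bleeding/spotting-free days".
- Bleeding/spotting: "One or more consecutive bleeding and/or spotting days where there are both bleeding and spotting days bounded on either end by 2 bleeding/spotting-free days".

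A free episode is the mirror image: "Two or more consecutive bleeding/spotting-free days bounded on either end by a bleeding or spotting day".

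The episode carries most of the later analysis. In 5.10.2.2 and 5.10.2.3 a day takes its scheduled or unscheduled status from the episode that contains it. In 5.10.4 the total, scheduled and unscheduled day counts are restricted to days lying "within the bleeding only, spotting only and bleeding/spotting episodes that start during the cycle of interest". The reference-period (RP) totals in 5.10.5 are restricted in the same way: "the number of spotting days within the bleeding only, spotting only and bleeding/spotting episodes that start during the RP of interest". Absence of scheduled bleeding means that no scheduled episode starts in the cycle. The RP endpoints also include the number of free episodes and "The mean duration of the bleeding and/or spotting free episodes".

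Two outputs bypass episodes and use diary days directly: absence of any bleeding or spotting in a cycle (5.10.4), and the daily bar chart (9.5.3.1).

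**The concern.** A single recorded free day between two runs has no stated place. It is too short to be a free episode, yet it breaks the run of consecutive days and deprives each neighbouring run of its two free days on that side. The rules in 5.15.2 do not help, because they fill missing or ambiguous entries and do not bridge a recorded 0.

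This conflicts with the SAP's own intent. Section 5.10.2.1 treats any bleeding or spotting in the expected non-bleeding period as unscheduled, and 5.10.2.2 says that all bleeding and spotting days will be classified. A day that belongs to no episode cannot be classified by the rules given.

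At stake is the bleeding-pattern objective. Bleeding days and unscheduled episodes would be under-counted and absence of scheduled bleeding overstated, including in the subgroup summaries set by 4.3. One cycle could show zero bleeding or spotting days and no episode, yet fail the test for absence of any bleeding.

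**Working it through.** The SAP gives no figure to reproduce, so the check applies Table 1 to constructed 91-day diaries, each treated as the whole record. Three rules are compared: two free days required at both ends, two free days at one end enough, and the proposed rule, under which only a gap of two or more free days ends an episode. Cells give episodes / days counted.

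| Diary | Days recorded | Both ends | One end enough | Proposed rule |
|---|---|---|---|---|
| Spotting 12-13 and 15-16 | 4 | 0 / 0 | 2 / 4 | 1 / 4 |
| Bleeding 26-27, spotting 29-30 | 4 | 0 / 0 | 2 / 4 | 1 / 4 |
| Spotting 40, 42, 44 | 3 | 0 / 0 | 2 / 2 | 1 / 3 |
| Bleeding 26-28, spotting 29 (unsplit) | 4 | 1 / 4 | 1 / 4 | 1 / 4 |
| Bleeding 26-27+29, 54-55+57, 82-83+85 | 9 | 0 / 0 | 6 / 9 | 3 / 9 |

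**First row by hand.** The run on Days 12-13 has Days 10 and 11 free before it, but after it Day 14 is free and Day 15 is spotting. The run on Days 15-16 has Days 17 and 18 free after it, but before it Day 14 is free and Day 13 is spotting. Each run is bounded on one side only.

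**Second row.** Days 29-30 are Days 1-2 of the next cycle, so the whole bleed lies inside the scheduled window. On the both-ends reading no scheduled episode starts, and the cycle is tabulated as having no scheduled bleeding.

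**Third row.** The middle day has only one free day on each side, so it is lost on both readings of the existing text.

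**End of the diary.** Under 5.1.2 and 5.15.2 the three days after Cycle 13 are imputed from the last recorded response. If Day 28 is a bleeding day, those three days become bleeding days as well. A bleed that starts on Day 25 then has no two free days after it: no episode on the both-ends reading, and an episode running through the imputed days on the one-end reading. Bleeding on the last recorded day before withdrawal is unbounded in the same way, because 5.15.2 imputes nothing after withdrawal.

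**Free episodes.** A diary with 91 free days contains no bleeding or spotting day to act as a bound. Both readings give 0 free episodes, so the mean free duration is undefined. On the both-ends reading the opening free stretch of every diary also fails, because 5.15.2 sets Days 1-7 of Cycle 1 to no bleeding and nothing precedes them.

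**Extreme case.** A woman with bleeding recorded daily from Day 8 to the end of the diary has, on the both-ends reading, 0 episodes, 0 counted days and 0 free episodes. A woman who never bleeds has the same three values.

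**The case against.** The best defence is that this is loose wording and not a rule meant to delete data. Sections 5.10.2.1 and 5.10.2.2 show that the authors expected every bleeding day to be classified, and a programmer might merge split runs without being told. Either end can also be read as one end, which keeps 4 of 4 days in the first two diaries. Protocol 12.6.1 refers to a published standardisation paper and to its own Table 1, and neither can be read in the text available, so a convention for single free days may exist there. The summaries are descriptive, in a study with no formal statistical analyses (SAP 9.0).

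Most of this stands as a limit on the consequence. It does not remove the defect: the same diary gives 0, 1 or 2 episodes according to the reading chosen, and neither reading of the current text keeps every day.

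A reader might infer more than the documents support:

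- **That these days vanish from every count.** They do not. Absence of any bleeding and the daily bar chart keep them.
- **That bleeding on the first diary day is unbounded.** Days 1-7 of Cycle 1 are set to no bleeding, so no episode can touch the first day.
- **That the mean free duration loses all its longest values.** Section 5.10.5 assigns an episode to the RP in which it starts and uses its full duration. If that covers free episodes, a stretch that crosses an RP limit is kept in full in its starting RP. Only stretches that are never bounded are lost.
- **That a percentage loss can be stated.** Any such figure depends on an assumed frequency of single-day gaps, and the documents give none. They also give no basis for saying that unscheduled spotting is hit hardest.

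**Conclusion.** The point holds in a limited form. On the both-ends reading, runs split by one recorded free day and bleeding still present on the last recorded day meet no episode definition. Their days drop out of all episode-based endpoints and day counts, contrary to 5.10.2.1 and 5.10.2.2. On the one-end reading most split runs are kept as separate episodes, but the middle of three alternating days is still lost. The result for a woman without bleeding, 0 free episodes and an undefined mean free duration, does not depend on the reading.

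Within a single diary the loss can be complete (0 of 4 and 0 of 9 days in the examples). Its size across the study is unknown. The direction on the both-ends reading is clear: fewer bleeding days and more apparent absence of scheduled bleeding. Contraceptive efficacy is unaffected. The text should be corrected, because a rule applied as written gives results that contradict other parts of the same plan.

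**What to change.** 1. In Table 1, define an episode as bleeding and/or spotting days with no interior gap of two or more free days. A single free day lies inside the episode but is not counted as a bleeding or spotting day. The 5.10.5 duration formula would then include it: Days 12-16 last 16 - 12 + 1 = 5 days, with 4 spotting days. The SAP should say so.
2. Let the end of the recorded diary act as a boundary for bleeding episodes and for free episodes, and let the start of the diary act as a boundary for free episodes.
3. In 5.10.5, report an RP with no bleeding or spotting as one free interval covering that RP. State how this fits with assignment by start date and use of full duration, so that a stretch crossing RPs is neither cut short nor counted twice without notice.
4. Keep the episode-based scheduled/unscheduled classification, which the SAP's amendment summary shows was a deliberate choice. Every bleeding and spotting day then has an episode from which to take its status.

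The cost is SAP wording in Table 1 and 5.10.5, with matching programming. The diary data are the same and no new collection is needed.

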5.10.2 Cycle analysis

5.10.2.1 Definition of cycles

In the cycle analysis of a 24/4 regimen of a COC, an up to 7-day vaginal bleeding is scheduled to occur in conjunction with the first inactive tablet (Day 25) and end on Day 3 of the next cycle (expected bleeding period). In principle, no vaginal bleeding is expected to occur at other times during the cycle. This means that the remainder of the cycle constituted the expected non-bleeding period of 21 days. Therefore, any bleeding/spotting that occurs during the expected non-bleeding period (starting on Day 4 of the actual cycle up to and including Day 24) are considered as unscheduled.

The following definitions (**Table 2**) will be used for the cycle analysis:

Table 2: Bleeding/spotting definitions used for the cycle analysis

Scheduled Bleeding/Spotting (Withdrawal Bleeding/Spotting)	Any bleeding/spotting that occurs during the hormone-free interval (i.e. Days 25 – 28) and continues through Days 1-3 of the subsequent active cycle. Note: any bleeding/spotting that occurs while taking active hormones during Days 1-7 of the first cycle will be imputed as no bleeding.
Unscheduled Bleeding/Spotting	Any bleeding/spotting that occurs while taking active hormones that does not meet the criteria for scheduled bleeding/spotting.
Unscheduled Bleeding	Any bleeding that occurs while taking active hormones that does not meet the criteria for scheduled bleeding.
Unscheduled Spotting	Any spotting that occurs while taking active hormones that does not meet the criteria scheduled spotting.
Early Withdrawal Bleeding/Spotting	Any bleeding/spotting episode that starts before the scheduled bleeding/spotting period and continues into the scheduled bleeding/spotting period.
Continued withdrawal bleeding/spotting	Any bleeding/spotting episode that starts in the scheduled bleeding/spotting period and continues after the scheduled bleeding/spotting period.

Based on these definitions, the cycle analysis of bleeding/spotting episodes will perform in two ways:

- a classical approach
- a modified cycle analysis

5.10.2.2 Classical cycle analysis

In the classical analysis, early and continued withdrawal bleeding are regarded as scheduled.

The following rules will be used for the classical approach to classify each bleeding only episode, spotting only episode or bleeding/spotting episode as scheduled or unscheduled:

The episode is defined as unscheduled, if any of the following criteria are met:

- The episode has a start date after Day 7 of Cycle 1 and an end date that is on or before Day 24 of Cycle 1
- For Cycles 2 to 13, the episode has a start date after Day 3 of the cycle and an end date that is on or before Day 24 of the cycle

The episode is defined as scheduled (withdrawal bleeding and/or spotting), if any of the following criteria are met:

- The episode has a start date after Day 24 of the cycle and an end date that is on or before Day 3 of the next cycle
- The episode has a start date after Day 24 of the cycle and an end date that is after Day 3 of the next cycle (continued withdrawal bleeding/spotting).
 - Note it is not possible to have continued withdrawal bleeding for Cycle 13 because data are not collected for Cycle 14
- The episode has a start date before Day 24 of the cycle and an end date on or after Day 25 (early withdrawal bleeding/spotting).

All bleeding days and spotting days will then be classified as scheduled or unscheduled based on whether the bleeding or spotting days are included in a scheduled or unscheduled episode using the rules in this Section above. A bleeding day or spotting day that occurs in a scheduled episode will be classified as scheduled and a bleeding day or spotting day that occurs in an unscheduled episode will be classified as unscheduled.

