5.10.2.3 Modified Cycle Analysis

In the modified cycle analysis, the definitions of expected non-bleeding and expected bleeding periods are strictly followed, i.e., all bleeding episodes that overlap with expected non-bleeding intervals are considered unscheduled. Thus in this analysis, the definitions of scheduled and unscheduled bleeding/spotting episodes presented in the Table 2 are also applicable, but early and continued withdrawal bleedings are regarded as unscheduled.

Therefore, in the derivation of endpoints where early and continued withdrawal bleeding are classed as unscheduled bleeding the following rules are used to classify each bleeding only episode, spotting only episode or bleeding/spotting episode as scheduled or unscheduled:

The episode is defined as unscheduled, if any of the following criteria are met:

- The episode has a start date after Day 7 of Cycle 1 and an end date that is on or before Day 24 of Cycle 1
- For Cycles 2 to 13, the episode has a start date after Day 3 of the cycle and an end date that is on or before Day 24 of the cycle
- The episode has a start date after Day 24 of the cycle and an end date that is after Day 3 of the next cycle (continued withdrawal bleeding/spotting)
 - Note it is not possible to have continued withdrawal bleeding for Cycle 13 because data are not collected for Cycle 14
- The episode has a start date before Day 24 of the cycle and an end date that is on or after Day 25 (early withdrawal bleeding/spotting)

The episode is defined as scheduled (withdrawal bleeding and/or spotting), if the following criterion is met:

• The episode has a start date after Day 24 of the cycle and an end date that is on or before Day 3 of the next cycle

All bleeding days and spotting days will then be classified as scheduled or unscheduled based on whether the bleeding or spotting days are included in a scheduled or unscheduled episode in the same way as outlined for the classical analysis but using the rules in this Section above where early and continued withdrawal bleeding are classed as unscheduled episodes.

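### In both cycle analyses the early-withdrawal rule stops one day short, so a bleeding episode that starts on Day 24 and runs into Day 25 is given no class

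*SAP*

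**What the plan says.** SAP 5.10.2.1 divides the cycle in two. The expected non-bleeding period is defined as "starting on Day 4 of the actual cycle up to and including Day 24". The scheduled period is Days 25–28 together with Days 1–3 of the next cycle. Table 2 in that section defines early withdrawal bleeding as "Any bleeding/spotting episode that starts before the scheduled bleeding/spotting period and continues into the scheduled bleeding/spotting period".

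Two rule lists then class each episode, and each bleeding or spotting day takes the class of its episode.

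- **Classical analysis (5.10.2.2).** The lead-in says: "In the classical analysis, early and continued withdrawal bleeding are regarded as scheduled". The unscheduled rule for Cycles 2 to 13 requires a "start date after Day 3 of the cycle and an end date that is on or before Day 24 of the cycle". The ordinary scheduled rule begins "The episode has a start date after Day 24 of the cycle and an end date that is on or before Day 3", where Day 3 belongs to the following cycle. Continued withdrawal also needs a start after Day 24. Early withdrawal is: "The episode has a start date before Day 24 of the cycle and an end date on or after Day 25".
- **Modified analysis (5.10.2.3).** The lead-in says that "all bleeding episodes that overlap with expected non-bleeding intervals are considered unscheduled". The early-withdrawal rule has the same boundary: "The episode has a start date before Day 24 of the cycle and an end date that is on or after Day 25".

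**The concern.** Day 24 is the last day of the expected non-bleeding period, so an episode that begins then and continues into Day 25 is early withdrawal bleeding under Table 2. The rule lists ask for a start strictly before Day 24, and no other rule picks the episode up.

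If the lists are programmed as written:

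- The episode is missing from the early-withdrawal count (SAP 9.5.3.1).
- In the classical analysis, a woman with no other scheduled episode starting in that cycle is counted as having no scheduled bleeding (SAP 5.10.4). The error carries into the cumulative table of absent withdrawal bleeding and the subgroup summaries (SAP 9.5.3.1).
- In the modified analysis, unscheduled episodes and days are undercounted.
- Scheduled plus unscheduled days no longer equal total days, although SAP 5.10.4 describes the total as their sum.

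**Working it through.** The plan states no figure on this point, so there is none to reproduce. The check applies the written rules to possible episodes.

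**Inputs.** The rules are those of SAP 5.10.2.2 and 5.10.2.3. Let s be the start day and e the end day, with Days 1–3 of the next cycle numbered 29–31. A 28-day cycle is assumed.

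| Rule | Condition as written | s = 24, e ≥ 25 |
|---|---|---|
| Unscheduled, Cycles 2–13 | s > 3 and e ≤ 24 | fails on e |
| Unscheduled, Cycle 1 | s > 7 and e ≤ 24 | fails on e |
| Scheduled | s > 24 and e ≤ 31 | fails on s |
| Continued withdrawal | s > 24 and e > 31 | fails on s |
| Early withdrawal | s < 24 and e ≥ 25 | fails on s |

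**Enumeration.** Starts run over the shifted cycle, from Day 4 (Day 8 in Cycle 1) to Day 31. Ends run up to Day 52, which is Day 24 of the next cycle.

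- Cycles 2–13: 49 + 48 + … + 22 = 28 × (49 + 22)/2 = 994 start–end pairs.
- Cycle 1: 45 + 44 + … + 22 = 24 × (45 + 22)/2 = 804 pairs.
- Unclassified as written: 52 − 24 = 28 pairs in each case, identical in the classical and modified lists. All start on Day 24 and end on Day 25 or later. No other start day leaves a gap, and no pair receives conflicting classes.
- With the early-withdrawal condition changed to s ≤ 24: 0 unclassified and 0 conflicting, in both lists and for all cycles.

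These are counts of rule combinations, not expected frequencies, and they depend on the chosen cap for the end day. One affected start day out of 28 does not depend on that cap.

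**Worked cases under the rules as written (Cycles 2–13).**

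| Episode | Total days | Classical | Modified |
|---|---|---|---|
| Days 23–28 | 6 | 6 scheduled | 6 unscheduled |
| Days 24–28 | 5 | 0 scheduled, 0 unscheduled | 0 scheduled, 0 unscheduled |
| Days 25–28 | 4 | 4 scheduled | 4 scheduled |

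An episode confined to Day 24 is not affected: it ends by Day 24 and is unscheduled in both analyses.

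**Effect on the percentages.** Let p be the share of evaluable cycles with an episode that starts on Day 24 and ends on Day 25 or later.

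- Early withdrawal is understated by p, because only one episode per cycle can span Days 24 and 25.
- Absence of scheduled bleeding (classical) is overstated by at most p, because some of these women have another scheduled episode starting in the same cycle.
- The percentage with any unscheduled episode (modified) is understated by at most p, for the corresponding reason.

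**The case against.** The strongest reply is that the SAP already classes this episode. The rule lists are built on the Table 2 definitions, each disputed rule carries the Table 2 label for early withdrawal, and the lead-ins say how to treat that category. In the modified analysis the lead-in alone settles the matter. This stands as evidence of intent. It does not make the rules right: they are the stated method for classing each episode, and a programmer who follows them gets a different answer from one who follows Table 2. Table 2's general definition of unscheduled bleeding does not close the gap either. It is limited to bleeding while active hormones are taken, so it does not reach Days 25–28, and in the classical analysis it would contradict the lead-in.

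A second reply is that the check reads one rule literally and another in context. The continued-withdrawal rule sets no upper limit on the start day, and the finding of no conflicting classes relies on confining starts to the shifted cycle. That is fair, and the result should be read with that condition. It does not rescue the Day 24 episode: a reading loose enough to make it continued withdrawal from the previous cycle would do the same to other mid-cycle episodes that the unscheduled rule covers.

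Third, nothing shows that the rules were coded literally. SAP 8.2 describes table runs reviewed before database lock, and SAP 10.0 refers to a separate quality control plan that is not available here. A check may already exist. The consequences are therefore conditional.

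**Conclusion.** The concern holds as a minor inconsistency. Both rule lists leave exactly one start day, Day 24, without a class when the episode continues into the scheduled period, and this contradicts Table 2 and both lead-in sentences. The intended class is not in doubt.

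The size in women or cycles cannot be computed, because the documents give no distribution of onset days; the effect is known only through p. It also rests on the rules being programmed as written. Early-withdrawal counts, classical absence of scheduled bleeding, modified unscheduled counts, and the scheduled/unscheduled split of days are open to error.

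Not affected are total days as counted in SAP 5.10.4, absence of any bleeding, the daily bar chart, the reference-period analysis and the Pearl Index. The affected outputs are descriptive summaries of other secondary variables (SAP 4.2.2), and SAP 9.0 plans no formal statistical analyses.

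**What to change.** In the early-withdrawal rule of both SAP 5.10.2.2 and 5.10.2.3, replace the start condition with *on or before Day 24*. A Day 24–28 episode then contributes 5 scheduled days in the classical analysis and 5 unscheduled days in the modified one, as Table 2 and the lead-ins require.

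Add a programming check that every episode receives exactly one class and that scheduled plus unscheduled days equal total days.

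The cost is the same wording change in two places and a line or so of checking code. No new data are needed and no definition changes in intent.
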